11.3.6 Time-to-Event Measures

Time to Local Recurrence- Defined as the duration of time from surgical resection of the primary tumor until local recurrence (amputated patients excluded).

Local Disease-Free Survival- Defined as the duration of time from surgical resection of the primary tumor until local recurrence or death, whichever occurs first.

Distant Disease-Free Survival - Defined as the duration of time from randomization until development of distant metastatic disease or death, whichever occurs first. Subjects with stage IV disease will be censored from this analysis.

Disease-Free Survival - Defined as the duration of time from surgical resection to local recurrence, distant metastatic disease, or death, whichever occurs first. Subjects with stage IV disease will be censored from this analysis.

Progression-Free Survival - Defined as the duration of time from randomization to progressive disease (per RECIST), local recurrence, distant metastatic disease (exclusive of stage IV subjects), or death, whichever occurs first.

Overall Survival - Defined as the interval of time from randomization until death from any cause.

11.4 Determining Response to Pazopanib for Continuing on Maintenance

Subjects who have a partial response by either RECIST 1.1 criteria on CT or MRI, and/or PERCIST 1.0 criteria by FDG PET after the 14 day Run-in period on pazopanib will have the option to remain on pazopanib for one year of therapy following surgery and adjuvant chemotherapy/radiation.

12.0 DATA MANAGEMENT/CONFIDENTIALITY

The Investigator will ensure that data collected conform to all established guidelines. Each subject is assigned a unique patient number to assure subject confidentiality. Subjects will not be referred to by this number, by name, or by any other individual identifier in any publication or external presentation. The licensed medical records department, affiliated with the institution where the subject receives medical care, maintains all original inpatient and outpatient chart documents.

Subject research files including paper and electronic case report forms, diagnostic pathology reports, and lab tests will be stored in a secure location that protects confidential information.

13.0 CORRELATIVE STUDIES

Plasma will be collected for measurement of VEGF and soluble VEGFR2 (sVEGFR2) at baseline, after the 14 day Run-in period of pazopanib, after completion of neoadjuvant chemotherapy and every 3 months thereafter until completion of pazopanib maintenance therapy, when indicated.

Quantitative enzyme-linked immunosorbent assays (ELISA) for VEGF and sVEGFR2 will be performed on plasma and tumor extracts.

MicroRNAs have been shown to be promising blood and tissue-based markers for cancer detection.[56] An extension of this is that such markers may also be excellent candidates for measuring response to therapy. There are currently no validated biomarkers to predict response to antiangiogenic therapy. Consequently, the ability to test candidate microRNA biomarkers before, during and after neoadjuvant systemic therapy offers an ideal setting to assess potential biomarkers. Blood samples will be collected for micro RNA at baseline, after the 14 day Run-in period of pazopanib, following neoadjuvant chemotherapy and every 3 months thereafter until completion of pazopanib maintenance therapy, when indicated.

Samples to be tested will be an additional 3 tablespoons of whole blood (23cc) at each time of clinical lab draw, collected as 10cc into EDTA tubes (plasma), 10cc into serum separator tubes, and 3cc into Tempus tubes (containing an RNA stabilizer).

There may also be evaluation of other potential predictive and prognostic markers using analysis of protein, DNA and RNA from surgical tumor tissue.

14.0 STATISTICAL CONSIDERATIONS

14.1 Analysis plan

The primary objective is to compare FDG SUV (SUV lean, SUL) measures for patients receiving pazopanib and placebo. The primary endpoint is the percent change in SUV between baseline and the end of the 14-day Run-in period of pazopanib or placebo. The comparison will likely be conducted using a two-sided Wilcoxon rank sum test, often used as a nonparametric alternative to the two-sample t-test for studies with a small sample size. Additional endpoints will include SUV percentage change between baseline and the end of preoperative therapy, absolute post-treatment SUV (at 14 days and following preoperative chemotherapy), and absolute difference in SUV.

The analysis sample for the primary pharmacodynamic analysis is expected to exclude patients who have incomplete data due to missed PET scans or due to study withdrawal for toxicity. However, reasons for missing data will be examined, and multiple imputation will be considered if patients with incomplete data would be considered as part of the target population for future development of pazopanib in sarcoma. However, insofar as sarcoma is heterogeneous, the sample size is small, and covariates are limited – multiple imputation may not be applicable.

These pharmacodynamic response measures will be compared to tumor response by RECIST criteria, using graphical displays. Continuous measures of pharmacodynamic response (percentage change in SUL; response assessed using MRI) will also be compared to the trough plasma pazopanib, using graphical displays and correlation coefficients to investigate dose-response relationships related to patients' differing metabolism of pazopanib.

Descriptive displays of preliminary clinical endpoints (pathologic response, progression-free survival, overall survival) will compare response for the pazopanib and placebo groups, and will investigate the relationship between early pharmacodynamic response (by PET) and clinical endpoints. Response of high-risk soft tissue sarcoma to neoadjuvant chemoradiation therapy was estimated as 52% (38% no residual tumor, 14% ≥ 95 pathologic necrosis) in a series of 496 patients.[9] A smaller series found only 13/46 (28%) with $< 10\%$ viable tumor in surgical specimens following a variety of neoadjuvant regimens.[51] To direct planning of future studies, we will measure the rate of complete pathological response defined as greater than 95% necrosis in the surgical excision specimen. A 90% Wilson (score) binomial confidence interval will be computed for the rate of complete pathological response.

There are no stopping rules planned for toxicity, but safety will be monitored continuously. All subjects who are registered and receive at least one dose of study drug will be included in the safety analysis.

All reported adverse events will be coded using the Cancer Therapy Evaluation Program (CTEP) Common Toxicity Criteria version 4.0. The number and percent of subjects reporting adverse events (all, severe or worse, serious and related) will be quantified. Listings will be provided for all on-study deaths and adverse events that lead to withdrawal from study. Narratives of all serious adverse events and deaths on-study will be provided.

Correlative study assays will be analyzed using descriptive statistics, generally comparing pazopanib and placebo groups. Correlation will also be evaluated between pazopanib trough concentrations and drug exposure over the dosing interval (area-under-the-concentration-curve, AUC) in subjects consenting to the full intensive pharmacokinetic visits.

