sarcoma patients at high risk of tumor recurrence.[51] Forty-six patients with high-grade localized extremity sarcomas were studied. Those with a baseline tumor maximum SUV of 6 or greater and less than a 40% decrease in FDG uptake after chemotherapy were at high risk for systemic disease recurrence, estimated to be 90% at 4 years. In contrast, those whose tumors had a 40% or more decline in the tumor maximum SUV after chemotherapy, were at significantly lower risk of recurrent disease and death following surgery and radiation. Interestingly, in this study the histologic response to chemotherapy did not correlate with patient outcome.

In this randomized study subjects will undergo baseline staging scans including FDG-PET. After the 14 day Run-in period of pazopanib versus placebo, and prior to commencement of preoperative chemotherapy, subjects will undergo repeat FDG-PET. After 2 cycles of chemotherapy FDG-PET will be repeated.

If results of this trial can be confirmed in larger trials, then this could establish that changes in tumor SUV in response to antiangiogenic therapy and to chemotherapy may distinguish those patients who are likely to benefit from these systemic therapies from those who will not.

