14.2 Sample size justification

If the standard deviation for percent change in is 20% and the average change is 0% for placebo and a 30% decrease for pazopanib, there will be approximately 90% power to detect a difference between the placebo and pazopanib group in average percent change for n=21 and a 2:1 randomization.

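### Section 14.1 plans no baseline-adjusted estimate or interval for any SUV comparison; the clear loss is in the absolute post-treatment SUV endpoint, not in the primary test

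*Combined protocol and SAP*

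**What the plan says.** Section 14.1 defines the outcome: "The primary endpoint is the percent change in SUV between baseline and the end of the 14-day Run-in period of pazopanib or placebo". The test is named with a hedge: "The comparison will likely be conducted using a two-sided Wilcoxon rank sum test". The further SUV endpoints are percent change to the end of preoperative therapy, together with "absolute post-treatment SUV (at 14 days and following preoperative chemotherapy), and absolute difference in SUV". No test is named for these, and no SUV comparison has a covariate, an effect estimate or a confidence interval. The only interval in Section 14.1 is the 90% Wilson interval for pathologic response.

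Other relevant statements:

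- Section 4.3 requires FDG-PET at screening, and Section 14.1 expects to leave out patients with missed scans. Everyone analysed should therefore have a baseline SUL.
- Section 6.0 randomizes 2:1 and names no stratification factor.
- Section 14.2 assumes an SD of 20 points for percent change and that "the average change is 0% for placebo and a 30% decrease for pazopanib". It concludes that "there will be approximately 90% power to detect a difference between the placebo and pazopanib group" with 21 patients. It states neither alpha nor the test behind the figure.
- Section 1.0 says the results will inform the design and feasibility of a larger trial.

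**The concern.** SUV varies between patients before any treatment. An endpoint that does not take out that variation carries it as noise. With 14 patients against 7, the arms can also differ noticeably at baseline by chance.

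Percent change removes baseline fully only if the change is proportional to it. Absolute post-treatment SUV does not remove it at all.

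A rank-sum test reported alone gives a p-value. A pilot that feeds a decision about a larger trial needs the size of the metabolic effect and its uncertainty. At stake are the precision of the SUV comparisons and the usefulness of the result, not the validity of the primary test.

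**Working it through.** **Inputs.** From Section 14.2: difference 30 points, SD 20, n=21 at 2:1, hence 14 and 7. Assumed, because the documents are silent: two-sided alpha 0.05, normal percent changes, equal SDs in the two arms, no losses from the 21, a within-arm correlation r between log baseline SUL and percent change, and the SD of log baseline SUL.

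**1. The plan's own figure.** SE = 20 × √(1/14 + 1/7) = 20 × 0.463 = 9.26. Then 30/9.26 = 3.24, and 3.24 − 1.96 = 1.28, which gives power 0.90. This reproduces Section 14.2 by the normal approximation. On the same inputs the t-test (19 df) has 0.867. The exact Wilcoxon test (attained alpha 0.046) has about 0.83 by simulation.

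**2. Chance imbalance and the primary endpoint.** The difference in mean baseline has a standard error of 0.463 SD, and the chance that it exceeds 0.5 SD is 28%. An imbalance of 0.5 SD shifts the unadjusted difference by r × 20 × 0.5, which is 3 points at |r|=0.3 and 5 points at 0.5, against a planned 30. Simulated Wilcoxon type I error is 0.045 to 0.047 for every r from 0 to 0.7. The imbalance is therefore noise and does not bias the test.

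**3. Power for the primary comparison.** Simulated:

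| Analysis | r=0 | \|r\|=0.3 | \|r\|=0.5 |
|---|---|---|---|
| Wilcoxon on percent change | 0.83–0.85 | 0.83–0.85 | 0.83–0.85 |
| t-test on percent change | 0.868 | 0.866 | 0.865 |
| ANCOVA of percent change on arm and baseline | 0.846 | 0.877 | 0.927 |
| ANCOVA of log SUL on arm and log baseline | 0.78 | 0.83–0.84 | 0.89 |

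For the log model, r is taken as negative (hotter tumours fall by a larger percentage). The log model is behind the Wilcoxon test at r=0, about level at 0.3 and ahead at 0.5.

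**4. Absolute post-Run-in SUV.** Take r=0, and let s be the SD of log baseline. The arm effect on the log scale is ln(0.70) = −0.357. The SD of the log ratio is about 0.20 on placebo and 0.20/0.70 = 0.286 on pazopanib. Pooled, this is √[(6 × 0.040 + 13 × 0.0816)/19] = 0.262. Without adjustment the SD of log post-Run-in SUV is √(s² + 0.262²).

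- s=0.3: SD 0.398; 0.357/(0.398 × 0.463) = 1.94; approximate power 0.49.
- s=0.6: SD 0.655; 0.357/(0.655 × 0.463) = 1.18; approximate power 0.22.
- Baseline removed: 0.357/(0.262 × 0.463) = 2.94; approximate power 0.84.

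Simulation allows for the rank test, the small sample and the estimated slope. It gives about 47% at s=0.3 and 20% at s=0.6 for the unadjusted rank comparison (46%, 25% and 16% at s=0.3, 0.5 and 0.7 in a separate run). ANCOVA has about 78% at any s.

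**5. Absolute difference in SUV.** The rank comparison has 80%, 77% and 72% at s=0.3, 0.5 and 0.7 with r=0. The loss here is small.

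**The case against.** The strongest case is that a rank test on percent change is a sound choice for 21 patients with a heterogeneous disease, and most of that stands.

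- A reader might infer that the plan ignores baseline. It does not: baseline is the denominator of the primary endpoint. Only residual dependence of percent change on baseline goes unadjusted.
- A reader might infer that the unadjusted comparison is biased. It is not: randomization protects it, and the type I error is kept.
- A reader might infer that ANCOVA should replace the primary test to recover power. The documents do not support this, because r appears nowhere in them. The ranking also depends on distribution. With heavy-tailed t(3) errors, Wilcoxon against ANCOVA of percent change was 0.941 against 0.885 at r=0, and ANCOVA led only at |r|=0.5 (0.924 against 0.907). With skewed errors Wilcoxon led throughout.
- Section 2.7 does not fill the gap. "Those with a baseline tumor maximum SUV of 6 or greater" describes patients who also had a limited decline after chemotherapy, and it concerns recurrence. It does not show that baseline predicts the 14-day percent change.

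It is also fair to say that the absolute-SUV measures are only additional endpoints with no named test, so an unadjusted rank comparison is the natural reading and not a stated one. A Hodges-Lehmann interval could accompany the Wilcoxon test without any model. Neither point answers the gap: as written, the plan provides no adjustment and no interval, and absolute post-treatment SUV is the endpoint that most needs adjustment.

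**Conclusion.** The point holds in a limited form. Section 14.1 describes no baseline-adjusted analysis and no effect estimate or interval for SUV, although the needed data are already collected.

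For the primary endpoint this is not an error. The Wilcoxon test is valid, and adjusting on the log scale could cost about 5 points of power (0.78 against 0.83) or gain about 6 (0.89 against 0.83) as |r| runs from 0 to 0.5.

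For absolute post-treatment SUV at 14 days the loss is large: about 47% down to 20% power unadjusted, against about 78% adjusted. These figures rest on alpha 0.05, r=0, a log-baseline SD of 0.3 to 0.6, normal percent changes and the Section 14.2 effect. The same reasoning applies after chemotherapy, but the documents give no effect or SD there, so no size is claimed.

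The larger trial described in Section 1.0 has progression-free and overall survival as endpoints. An SUV interval would inform the decision to proceed but would not by itself size that trial.

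**What to change.** In Section 14.1:

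1. Fix the Wilcoxon rank-sum test on percent change as the primary analysis and remove the hedge.
2. Prespecify a supporting ANCOVA of log(post-Run-in SUL) on arm and log(baseline SUL). Report the back-transformed percent difference with a 95% CI and a re-randomisation p-value for the arm coefficient.
3. Use the same baseline-adjusted model at 14 days and after chemotherapy in place of unadjusted comparisons of absolute post-treatment SUV and absolute difference.

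The cost is SAP wording and one degree of freedom, with no new data. Two consequences should be stated. The supporting estimate is a ratio of geometric means, not the difference in average percent change on which Section 14.2 is sized. The re-randomisation test must follow the actual allocation scheme, so the SAP should describe that scheme, including how the replacement patients in Section 7.8 are allocated. The simulated ANCOVA power uses the model's t statistic; the re-randomisation version was not simulated separately.

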The randomized, phase III study in STS subjects provided a key comparison of safety with pazopanib compared to placebo.[34] The most common AEs reported in $\geq 20\%$ of subjects in the pazopanib arm were fatigue (65%), diarrhea (59%), nausea (56%), weight decreased (51%), hypertension (42%), anorexia (40%), hair color change (depigmentation; 39%), and vomiting (34%), tumor pain (30%), dysguesia (28%), gastrointestinal pain (24%), headache (23%), musculoskeletal pain (23%), myalgia (23%), and dyspnea (20%). Most of the events were grade 1 or 2. A higher number of grade 3 AEs were reported in the pazopanib arm (63%) compared with the placebo arm (28%). The most frequent grade 3 AEs in the pazopanib arm were increased alanine aminotransferase (ALT), increased aspartate aminotransferase (AST), hypertension, and diarrhea. The frequency of grade 4 and grade 5 AEs was similar between the pazopanib and placebo arms: grade 4 in 7% and 6%, respectively; grade 5 in 4% and 3%, respectively.

When pazopanib was compared with sunitinib in 1102 subjects (554 subjects taking pazopanib and 548 subjects taking sunitinib), the frequency of AEs was similar (>99% in both). The safety profiles observed between the treatment arms were different, with greater frequency of diarrhea (63% pazopanib, 57% sunitinib) and hypertension (47% pazopanib, 41% sunitinib). Subjects who took pazopanib when compared with subjects taking sunitinib experienced lower frequency of fatigue, nausea, dysguesia and palmar-plantar erythrodysesthesia (PPE) syndrome. Grade 3 and 4 reported adverse events were similar between treatment arms, adding no comparative risk. However, grade 3 AEs of increased

ALT; increased ASP and headache occurred more frequently in the pazopanib arm when compared with the sunitinib arm. [34]

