Pazopanib is metabolized primarily by CYP3A4, and systemic exposure to pazopanib is altered by inhibitors and inducers of this enzyme. The concomitant use of strong CYP3A4 inhibitors should be avoided. Grapefruit may also increase plasma concentrations of pazopanib and should be avoided. CYP3A4 inducers such as rifampicin may decrease plasma concentrations; therefore, an alternative concurrent medication with none or minimal enzyme induction should be used.

Concomitant medications that have narrow therapeutic windows *and* are substrates of CYP3A4, CYP2D6 or CYP2C8 should be used with caution. If possible, medications that are not substrates for these enzymes and/or do not have narrow therapeutic windows should be substituted.

Pazopanib is a substrate for P-glycoprotein (P-gp) and BCRP transporters.

Dose Selection

Pharmacodynamic data indicate that pazopanib, at a monotherapy dose of 800 mg once daily, results in effects consistent with inhibition of the VEGF receptors and angiogenic factors.[34] Concentration-effect relationships were observed between trough plasma pazopanib concentrations and the development of hypertension as well as the percent change from baseline to the nadir of soluble VEGFR2 (sVEGFR2), a marker of VEGFR inhibition. Decreases in sVEGFR2 have been correlated with increased clinical benefit in RCC with other small molecule TKIs.[44] The trough plasma pazopanib concentrations associated with the EC₅₀ in both concentration-effect relationships were similar (15.3 mcg/mL for hypertension and 21.3 mcg/mL for sVEGFR2). Pazopanib monotherapy has been approved as an 800 mg once daily dose for the treatment of advanced RCC in the US.

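### Section 14.1 makes a complete-case sample the default for the primary PET comparison, with no committed as-randomised or sensitivity analysis, so losses related to toxicity can bias the SUV effect in either direction

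*Combined protocol and SAP*

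**What the plan says.** Section 14.1 sets out the primary comparison: "The primary endpoint is the percent change in SUV between baseline and the end of the 14-day Run-in period of pazopanib or placebo". On the method it says: "The comparison will likely be conducted using a two-sided Wilcoxon rank sum test".

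The sample for that comparison "is expected to exclude patients who have incomplete data due to missed PET scans or due to study withdrawal for toxicity". Two qualifications follow. Reasons for missing data will be looked at, and multiple imputation will be considered if the patients concerned would belong to the future target population. The paragraph then gives reasons (heterogeneous disease, small sample, few covariates) why "multiple imputation may not be applicable". No other handling of missing scans is named.

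Three other places bear on the point:

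- **Sections 7.8 and 11.0.** Under Section 7.8, a patient who received less than 80% of the intended doxorubicin, ifosfamide and pazopanib is not evaluated for the primary endpoints. Section 11.0 sets the 80% condition for all three drugs over the first two chemotherapy cycles. Section 7.8 also replaces patients withdrawn before surgery with newly randomised ones.
- **Section 7.7.1 (Table 1), Section 7.8 and Appendix A.** For many toxicities Table 1 stops the drug but continues follow-up. Section 7.8 separates stopping therapy from study withdrawal and asks for End of Treatment evaluations in willing patients. Appendix A schedules FDG-PET at the end of week two.
- **Section 2.4.** In the placebo-controlled sarcoma study, grade 3 adverse events were reported in 63% on pazopanib and 28% on placebo.

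**The concern.** The primary analysis is a randomised comparison, and its default sample is defined by something that happens after randomisation and that treatment can cause. If patients leave for toxicity more often on pazopanib than on placebo, the two analysed groups are no longer the groups that were randomised.

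The loss need not be neutral. Section 2.4 reports that "Concentration-effect relationships were observed between trough plasma pazopanib concentrations and the development of hypertension" and that trough concentration was also related to the fall in sVEGFR2. Toxicity and pharmacodynamic effect may therefore share a driver. Patients lost to toxicity could be high-exposure patients with large SUV declines, or patients who stopped too early to show any. Nothing in the documents fixes the sign.

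The wording also leaves open who is excluded. Section 7.8 lists only study closure and the patient's decision as criteria for study withdrawal, whereas Section 14.1 speaks of study withdrawal for toxicity.

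At stake is the estimate that Section 1.0 intends for the design of a larger trial. With 14 pazopanib patients, one or two exclusions move it, and the choice to impute or not would be made after the missing data are known.

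**Working it through.** **Inputs.** From Section 14.2: "If the standard deviation for percent change in is 20% and the average change is 0% for placebo and a 30% decrease for pazopanib", with n=21 and 2:1 allocation, so 14 pazopanib and 7 placebo. Planned enrolment in Section 14.3 is also 21, and Section 14.2 makes no dropout allowance. The documents state no alpha; two-sided 0.05 is assumed. They give no run-in withdrawal rate, so the number lost (k) and the mean change of those lost (m) are assumptions.

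**Step 1. The plan's own power.** Standard error of the difference = 20 × √(1/14 + 1/7) = 9.26. Then 30 / 9.26 = 3.24, and power = Φ(3.24 − 1.96) = 0.90. This reproduces the stated figure of about 90%. It is a normal approximation; simulation of the exact Wilcoxon test with normal data gives about 0.84.

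**Step 2. How many losses are plausible.** At assumed run-in withdrawal rates of 5%, 10% and 20% on pazopanib, the expected losses are 14 × rate = 0.7, 1.4 and 2.8. The chance of at least one is 1 − (1 − rate)^14 = 51%, 77% and 96%. A range of 1 to 3 is used below.

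**Step 3. Shift in the pazopanib mean.** Suppose the analysed patients average −30%. The as-randomised mean is then [(14 − k) × (−30) + k × m] / 14.

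- k=1, m=0: 13 × (−30) / 14 = −27.9
- k=2, m=0: 12 × (−30) / 14 = −25.7
- k=3, m=0: 11 × (−30) / 14 = −23.6
- k=2, m=−50: (−360 − 100) / 14 = −32.9

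The complete-case mean is −30 throughout. The gap is 2.1, 4.3 or 6.4 points in one direction and 2.9 points in the other. If those lost resemble those kept (m=−30), the mean does not shift.

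**Step 4. Power with two pazopanib patients affected** (exact Wilcoxon, simulated, without replacement):

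- excluded (12:7): about 0.80
- kept with half the effect (−15%): about 0.77
- kept with no change: about 0.67

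**Step 5. Would a scanned early stopper be analysed?** Such a patient has the end-of-Run-in scan, so Section 14.1 does not clearly exclude them. Section 7.8 does, if the dose is low enough. Counting run-in doses only (the rule does not say how the dose is counted), 11 of 14 is 79% and 12 of 14 is 86%. A patient who stopped after 11 or fewer full doses would not be evaluated for the primary endpoint, scan or no scan.

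**Step 6. Share of losses on pazopanib.** With equal withdrawal rates, 2:1 allocation alone puts 2/3 = 67% there. If withdrawal were proportional to the cited grade 3 rates (an assumption), the share would be 2 × 63 / (2 × 63 + 28) = 82%. A majority by count is therefore no evidence of bias. Differential loss needs a difference in rates, which the documents do not quantify for a 14-day run-in.

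**The case against.** The strongest case against has five parts.

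- **Only incomplete data are excluded.** A reader might infer that Section 14.1 estimates the effect only in patients who tolerate the drug. The text does not say that: a patient with toxicity who stays on study and is scanned is not excluded by this section. That stands. What can remove an early stopper who was scanned is the 80% rule, so a change to Section 14.1 alone would not be enough.
- **The safety figures are indirect.** A reader might infer that losses will fall mostly on pazopanib. The 63% and 28% are grade 3 events, not withdrawals, in a study not limited to 14 days. Grade 4 (7% and 6%) and grade 5 (4% and 3%) rates were similar. This stands, and higher loss on pazopanib remains plausible rather than shown.
- **The plan does address missing data.** Reasons are to be examined and imputation considered, and the protocol's follow-up provisions already allow the scan. This is fair, but none of it commits to an analysis.
- **A late scan may measure washout.** Section 2.4 gives a mean half-life of 30.9 h. Someone who stopped on day 5 and was scanned on day 14 would be 9 × 24 / 30.9 = 7 half-lives from the last dose. For a pilot pharmacodynamic question, an on-drug estimate has value. This stands as a cost, and as a reason to keep that analysis as supportive.
- **The shifts are small against the noise.** Gaps of 2.1 to 6.4 points are 0.2 to 0.7 of the standard error of 9.26, and replacement restores numbers. Both are true, but replacement does not restore the randomised comparison, and a systematic shift does not shrink with more patients.

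**Conclusion.** The point holds in a limited form. Complete-case is the default for the primary randomised comparison, the exclusion can depend on treatment, and no as-randomised or sensitivity analysis is committed.

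Under the plan's own effect and SD, losing 1 to 3 of 14 pazopanib patients would put the complete-case mean about 2 to 6 points from the as-randomised mean if those patients had no change. It would be about 3 points the other way for two strong responders at −50%. The loss counts and the outcomes of those lost are assumptions. The documents do not support a claim that the effect will be overstated, because the direction is unknown.

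This is a cheap improvement to the plan, not a fatal flaw.

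**What to change.** 1. In Section 14.1, state that the end-of-Run-in PET already scheduled in Appendix A is sought before chemotherapy in every randomised patient who has a baseline PET and remains willing, including those who stopped the run-in drug early. State that every such scan is analysed in the assigned arm as the primary analysis.
2. Reconcile Section 14.1 with the 80%-dose rules in Sections 7.8 and 11.0, so that those rules do not remove these patients from the day-14 endpoint.
3. Report the number of missing end-of-Run-in scans, and the reasons, by arm.
4. For scans that cannot be obtained, prespecify a sensitivity analysis in both directions, for example 0% change and a strong-responder value. This replaces the choice about imputation made after the missing data are seen.
5. Keep the complete-case or on-drug analysis as supportive.

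**Cost.** Wording in Sections 14.1, 7.8 and 11.0, and no newly scheduled scan. Scans after early stopping will partly reflect washout, so the estimate and the power may be somewhat less favourable. In the two-patient example, power moves from about 0.80 to between 0.67 and 0.77.
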